Evidence that these biomarkers are mediators of pregnancy outcomes that are affected by smoking has important implications for other pharmacotherapy studies in pregnant smokers by providing surrogate measures of potential risk [46] or in studies of reduced-exposure products (e.g., e-cigarettes, smokeless tobacco) that may be used by pregnant women. Since the FDA has recently been authorized to regulate tobacco products [56] there is likely to be heightened interest in biomarkers of tobacco product risk, particularly in vulnerable populations.

3. Hypotheses, aims and objectives:

Hypothesis 1:

We hypothesize that the nicotine inhaler compared to placebo inhaler will double the 7-day point prevalence abstinence rates (confirmed by exhaled CO) at 32-34 weeks gestation and will reduce the number of cigarettes smoked per day (CPD).

Aims / objectives 1:

To examine the efficacy of the nicotine inhaler compared to a matched placebo for smoking cessation and reduction among pregnant smokers.

Hypothesis 2:

- a) The nicotine inhaler will yield lower cotinine concentrations than placebo at 32-34 weeks gestation.
- b) Infants born to mothers in the NRT group will have higher birth weights and greater gestational age than infants born to mothers randomized to placebo. 2c) Fewer nicotine-treated subjects will deliver a low birth weight (<2500 grams) or a preterm (<37 weeks) infant than those in the placebo group.

Aim/Objective 2:

To compare the nicotine inhaler with placebo on safety measures which include a) overall nicotine exposure (i.e., serum cotinine) and b) birth outcomes (i.e., birth weight and gestational age).

Hypothesis 3: Pregnant women who are heavier smokers (i.e., ≥ 10 cigarettes/day) will be less able to quit with behavioral treatment alone than lighter smokers and the inhaler will increase cigarette abstinence more in heavier smokers.

Aim/Objective 3: To identify factors that determine which women benefit most from the use of nicotine inhaler for smoking cessation during pregnancy

Hypothesis 4: We hypothesize that birth weight will be negatively correlated with CPD and exhaled CO at the end of pregnancy, and that smoking cessation or reduction in the third trimester will explain the effect of treatment group on birth weight. We will also explore the interrelations among birth outcomes, tobacco exposure, and other promising biomarkers.

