Aim/Objective 4: To explore mechanisms by which the nicotine inhaler increases birth weight and gestational age.

4. Study Design & Procedures:

Study design: This is a randomized, double blind, placebo-controlled trial of the safety and efficacy of the nicotine inhaler in combination with behavioral counseling for smoking cessation during pregnancy. A total of 360 pregnant smokers will receive nicotine or placebo inhaler medication (1:1 ratio) for 6 weeks followed by a 6-week taper, with double-blind treatment conditions maintained throughout the study. Smoking cessation counseling and medication will be provided by a nurse at each ambulatory clinic. Nurses will be closely supervised by a psychologist with extensive expertise in smoking cessation ([name]), an obstetrician ([name] or [name]), and [name].

Overview of the behavioral intervention: The behavioral intervention, which will be utilized in both arms of the proposed study, exceeds many of the augmented interventions described in the USPHS guidelines [38]. The behavioral counseling will include a 35-minute counseling sessions at each of the first two visits, and 10 minutes of smoking cessation counseling at subsequent visits, delivered by the study nurses.

Overview of pharmacotherapy intervention: We will administer a 6-week course of therapy, consistent with instruction on the package insert. Dosage recommendations are based on the literature and on our pilot data, and will vary according to the level of maternal smoking. Pfizer Pharmaceuticals has agreed to supply us with nicotine inhaler and placebo treatments (see letter of support). To enhance compliance and to confirm patient reports and proper inhaler use, subjects will be asked to keep a daily diary of the number of cartridges used and to return all cartridges at the next study visit. Subjects will be instructed to bring medication and empty cartridges to next visit when they receive their reminder telephone call regarding upcoming appointments. For convenience, subjects will receive a plastic container to transport study drug. At Visit 5 (6 week visit), patients will be instructed on an individualized basis to taper their use over the next 6 weeks. If a study subject does not quit smoking

Nicotine Replacement for Smoking Cessation during Pregnancy

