Visits 7 & 8: 1- and 6-month postpartum follow-up visits will be completed to assess smoking relapse. We have chosen these time points because the majority of post-partum relapses occur during this period [18]. To reduce subject burden visit 7 will be done by phone. If unable to contact participant, the chart will be reviewed for smoking status.

Visit 7 (1 month postpartum +/- 7 days). The following items will be assessed by research nurse or study coordinator via a telephone call. Nicotine Use survey

1. Counseling to encourage abstinence postpartum

Visit 8 (approximately 6 months postpartum +/- 14 days). The following items will be assessed by research nurse or study coordinator.

1. Nicotine Use survey
2. Exhaled CO measurement if visit is attended
3. Counseling to encourage abstinence postpartum

As a back-up plan, study staff (not R.N.) will perform study procedures at visits that do not require study drug dispensement (Visits 1, 3, and 6). In this instance, the R.N. will complete the behavioral counseling via the telephone.

Sample size and justification:

Aim 1: Based on our nicotine gum study, we estimate that the quit rate will be 14.9% in the placebo group and 26.9% in the nicotine inhaler group (consistent with an odds ratio of 2.1 obtained in meta-analyses of inhaler effects in non-pregnant smokers [2]. Thus, 360 women (180 in each of the treatment group) would yield power of 0.80 to detect a significant difference using a two-tailed test and $\alpha=0.05$. Thus, 360 women (180 in each of the treatment group) would yield power of 0.80 to detect a significant difference using a two-tailed test and $\alpha=0.05$.

Nicotine Replacement for Smoking Cessation during Pregnancy

Aim 2: Using data from our completed study, a total of 226 subjects will yield power=0.80 (two-sided $\alpha=0.05$) to detect a difference of 100 ng/mL (SD=360) in the reduction in cotinine concentrations between groups. In our completed study (N=194), we observed a difference in birth weight of approximately 300 grams (SD 607), which was highly significant. Assuming a comparable effect size, we will have more than adequate power to detect birth weight differences between groups. Thus, our sample size of 360 is more than sufficient for this aim.

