Specific Aim 2.a: To compare effects of the nicotine inhaler with placebo on overall nicotine exposure (i.e., measured as serum cotinine), and birth outcomes [i.e., birth weight, gestational age, % of subjects who deliver a LBW (<2500 g) or preterm (<37 wk gestation) infant]. We will use a linear mixed model (see above) to determine whether cotinine concentration changes differentially over time by treatment group.

Specific Aim 2.b: Birth Outcomes. Mean birth weight will be compared for treatment groups using a two-sample t-test, or analysis of covariance if necessary to adjust for imbalances in patient characteristics. We will also compare the percentage of subjects in each group who deliver an infant of LBW (1500-2500 g) or preterm delivery using chi square or logistical regression.

Specific Aim 3: To determine which subjects benefit most from NRT, we will use logistic regression to examine the following predictors of treatment response (i.e., smoking cessation at 6 or 32 wks

Nicotine Replacement for Smoking Cessation during Pregnancy

gestation): pretreatment CPD, FTND score, perceived stress, motivation to quit, self-efficacy, treatment group, and the interaction of treatment group and the other independent (i.e., potential moderator) variables. **Analyses:** First, we will use a stepwise procedure to choose predictor variables and interaction terms that are significant ($\alpha=0.05$). A significant interaction between treatment group and other variables (e.g., pretreatment CPD) implies that the regression coefficients for this variable are not homogeneous with respect to the efficacy of the medication. The Johnson-Neyman procedure [79], which yields values of the continuous moderator variable at which the treatment groups differ significantly on the dependent variable, will be used to determine the “break point” nicotine inhaler efficacy. In our completed study[1], the effect of nicotine gum appeared to depend on CPD during the pretreatment period. For light smokers, the cessation rates were 18% and 21% for the control and nicotine groups, respectively, while for heavy smokers the rates were 0% and 15%, respectively. Since a similar effect in a sample of 150 women would provide power=0.80, using a two-sided $\alpha=0.05$, our proposed sample of 360 pregnant smokers will provide more than adequate power to detect the effect.

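### Aim 2, cotinine: on the stated 100 ng/mL and SD 360, 226 women give power of about 0.55, not 0.80, and the planned 360 give about 0.75

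*Combined protocol and SAP*

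**What the plan says.** Under *Sample size and justification*, Aim 2, the plan states that "a total of 226 subjects will yield power=0.80" at two-sided alpha 0.05, "to detect a difference of 100 ng/mL (SD=360) in the reduction in cotinine concentrations between groups". It attributes these values to the investigators' completed nicotine gum trial. The same paragraph turns to birth weight: "we observed a difference in birth weight of approximately 300 grams (SD 607), which was highly significant". It closes with one sentence on the whole aim: "Thus, our sample size of 360 is more than sufficient for this aim".

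Allocation is 1:1 (*Study Design & Procedures*). Hypothesis 2a sets the cotinine comparison at one time: "The nicotine inhaler will yield lower cotinine concentrations than placebo at 32-34 weeks gestation". The analysis section, Specific Aim 2.a, says: "We will use a linear mixed model (see above) to determine whether cotinine concentration changes differentially over time by treatment group". No within-woman correlation, baseline adjustment or allowance for missing samples enters the Aim 2 calculation.

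**The concern.** One sentence gives the difference, the SD, the alpha, the total number and the power, so it can be checked without outside information. A difference of 100 against an SD of 360 is a little over a quarter of a standard deviation. Differences of that size usually need about 200 women per arm, well above the 113 per arm implied by 226.

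The error affects the conclusion as well as the intermediate number. The plan reasons that 226 would be enough, so 360 must be ample. If 226 is wrong, that step fails, and whether 360 is enough for cotinine has to be worked out afresh.

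Cotinine is the nicotine-exposure safety measure in Aim 2 and the subject of Hypothesis 2a. A reader who accepts the paragraph would take a non-significant group difference as coming from a test with well over 80% power. On the stated inputs, the chance of missing the planned difference is about one in four even with complete data.

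**Working it through.** **Inputs.** From *Sample size and justification*, Aim 2: difference in cotinine reduction 100 ng/mL, SD 360, two-sided alpha 0.05, target power 0.80, stated total 226; birth weight difference 300 g, SD 607. From *Study Design & Procedures*: 1:1 allocation, 360 women (180 per arm).

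**Number needed on the stated inputs.** Standardised difference d = 100/360 = 0.278. The normal approximation is

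n per arm = 2 × (1.960 + 0.842)² / d² = 15.70 / 0.0772 ≈ 203.5,

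so 204 per arm, 408 in total. The t-test (noncentral t) gives 204.4, so 205 per arm, 410 in total. The stated 226 is 226/410 = 55% of that.

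**Power at given totals** (t-test, two-sided 0.05):

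| Total N | Power for 100 ng/mL, SD 360 |
|---|---|
| 226 (stated) | 0.547 |
| 360 (planned) | 0.748 |
| 410 | 0.801 |

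**Other readings of 226.**
- One-sided alpha: power 0.669 at 226; 322 women needed for 0.80 (normal approximation).
- 226 per arm: power 0.838, and the text says it is a total.
- 2:1 or 3:1 allocation: 459 or 544 women needed (normal approximation).
- One-sample or paired formula: about 104.
- 408 inflated for 25% dropout: 408/0.75 = 544.

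None of these gives 226 at power 0.80.

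**What would give power 0.80.**
- At N = 226: a difference of 135 ng/mL with SD 360, or an SD of 267 for 100 ng/mL.
- At N = 360: a difference of 107 ng/mL with SD 360, or an SD of at most 338 for 100 ng/mL.

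**If 360 is a single-visit SD** rather than the SD of the reduction, with baseline-to-follow-up correlation r and one follow-up value:
- Change score: SD = 360 × √(2(1 − r)). Setting this to 267 gives r = 0.72; setting it to 338 gives r = 0.56.
- Baseline-adjusted: SD = 360 × √(1 − r²). Setting this to 267 gives r = 0.67; setting it to 338 gives r = 0.35.

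So 226 needs r of about 0.7, while 360 needs a more modest value. The documents give no r.

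**Missing samples (assumption only).** The documents give no cotinine completion rate. With 90% of 360 (324 women) power is 0.70; with 75% (270 women) it is 0.62. The 75% matches the overall data-collection rate reported for the earlier trial under *Incentives*, which is not specific to cotinine.

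**Birth weight.** d = 300/607 = 0.494. Power at 360 is 0.997, and 130 women in total would give 0.80 (normal approximation). The claim of ample power is correct for this outcome.

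**Aim 1.** 14.9% against 26.9% with 180 per arm gives power 0.802, so the calculation that sets N = 360 reproduces.

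**The case against.** The strongest reply is that a two-sample t-test on one follow-up value is not the planned analysis. The plan uses a linear mixed model, and the schedule lists cotinine at baseline and at Visits 2, 5 and 6. Suppose 360 is the SD of a single-visit change, the random-intercept structure described for Aim 1 holds, and the treatment contrast averages k post-baseline visits. The effective SD is then 360 × √((1 + 1/k)/2), which is 312 for two visits and 294 for three. Power at 360 becomes 0.86 or 0.90, and the adequacy claim would stand for cotinine.

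This shows that 360 could be enough under a different contrast, but it does not support the text. The averaged contrast is not described anywhere. Hypothesis 2a concerns 32-34 weeks alone, where averaging over visits gains little. The descriptions of Visits 5 and 6 say serum goes for cotinine analysis only if the nurse identifies a significant change in smoking or inhaler use, so complete values at those visits cannot be assumed. Even under this reading, 226 women give only 0.67 or 0.72.

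It is also fair to say that the wrong figure cannot be identified from the documents. The SD may be misprinted, or a correlation may have been used and left out. That affects the order of the remedy: confirm the inputs first, then restate the power.

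Finally, the practical effect is limited. Cotinine is not the primary outcome, Aim 1 sets the sample size, and the individual rule on a 40% rise in cotinine does not depend on group power. All of this is accepted.

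**Conclusion.** The concern holds. On the plan's own inputs, 226 women give power of 0.55 rather than 0.80, and the planned 360 give 0.75 with complete data, so 360 is not more than sufficient for cotinine. For birth weight it is.

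This rests on reading 360 as the SD of the reduction, as the sentence is worded, and on a comparison of one follow-up value between two equal arms. A smaller SD, or a stated within-woman correlation, could change the cotinine result. The shortfall at the planned number is modest (0.75 against 0.80). It is larger if samples are missing, by an amount the documents do not allow one to fix. The primary aim and the total of 360 are unaffected. The text should be corrected because it misstates the power of a named safety comparison.

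**What to change.** First, go back to the source of the 226. If it came from a different SD, or from a baseline correlation or a multi-visit contrast in the mixed model, state that value and the contrast, and recompute power at 360.

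If SD 360 is indeed the SD of the reduction, replace the claim of 226 women and power 0.80 with wording such as: 360 women give power of about 0.75 to detect a difference of 100 ng/mL in the reduction in cotinine (SD 360, two-sided 0.05), or 0.80 to detect about 107 ng/mL.

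In either case, limit the closing statement of ample power to birth weight unless the recomputed cotinine figure supports it. If an allowance for missing cotinine samples is added, label the rate as an assumption.

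The cost is two sentences of text and, on the stated SD, a less favourable power figure for cotinine. No extra women are needed, and Aim 1 does not change.
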